## **9.4 Timeline for Reporting of Adverse events, Serious Adverse Events, Unexpected Adverse Events and Unanticipated Problems**

All serious adverse events, all unexpected adverse events, and all unanticipated problems will be reported to the IRB and DSMC as per standard operating procedure by phone, email or SAE form regardless of attribution.

## **9.5 Reporting Events to Local Institutional Review Boards**

All serious adverse events will be reported to the institutional review board (IRB). Each site will comply with their institution's standard operating procedures for reporting adverse events. Subjects will be instructed to report any adverse event(s) during the study and post-study. The investigator will

notify the IRB and any other applicable regulatory agency of any unanticipated death or adverse event occurring after a participant has discontinued or terminated study participation that may reasonably be related to the study.

## 9.6 Data Safety Monitoring Committee (DSMC)

This study will be reviewed by the Medical College of Wisconsin Cancer Center Data Safety Monitoring Committee (MCW CC DSMC). A summary of the MCW CC DSMC activities are as follows:

- Review the clinical trials for data integrity and safety
- Review all adverse events requiring expedited reporting as defined per protocol
- Review all DSM reports
- Submit a summary of any recommendations related to study conduct
- Terminate the study if deemed unsafe for patients

A copy of the MCW CC Data and Safety Monitoring Plan and membership roster will be maintained in the study research file and updated as membership changes. The committee will review reports from the study PI twice annually (or more frequently if needed) and provide recommendations on trial continuation, suspension or termination as necessary. Any available DSMC letters will be submitted to the IRB of record as required.

## 9.7 Potential Risks to Volunteer

### Likely:

**Blood Sampling:** Venipuncture can cause pain and discomfort at the needle puncture site

**Physical Exam:** Pain associated with movement of arm and assessment of swelling.

**Anticoagulation:** Use of injected anticoagulation can cause pain and bruising at the injection site. Cost associated with anticoagulation will be the responsibility of the participants and/or their insurance companies. The cost of enoxaparin (lovenox) will range in price from \$24 to \$119 a dose depending on the dosage necessary for each person. The cost of direct oral anticoagulant treatment averages \$11-15 a dose. The amount of

insurance copays will depend on the insurance plan. Some insurance companies do not cover costs associated with research studies.

Use of aspirin, clopidogrel (Plavix) and NSAIDs [ex. ibuprofen (Motrin), naproxen (Aleve)], while using anticoagulation will increase your risk of bleeding. The physician prescribing aspirin, clopidogrel or NSAIDs will determine if these medications should be continued while you receive enoxaparin or direct oral anticoagulant therapy. If needed, aspirin, clopidogrel, and NSAIDs can be safely resumed the day after anticoagulation is discontinued.

Due to risk of bleeding, spinal procedures should be avoided while using anticoagulation.

**Less Likely:**

**Blood Sampling:** Venipuncture can cause, bruising, fainting or local infection at the needle site.

**Survey:** Filling out the surveys could cause stress or anxiety to the participant

**Physical Exam:** Examining the chest cause participant embarrassment

**Anticoagulation:** Use of anticoagulation is known to cause an increased risk of bleeding that can occur at the injection site or systemically. Use of anticoagulation is known to cause an increased risk of bleeding that can occur at the injection site or systemically. Participants will have had anticoagulation for 0-6 months prior to catheter removal and one month after catheter removal. Usual care would include anticoagulation between 1-3 months after catheter removal. With a shortened course of anticoagulation, an increased risk of thrombosis or post-thrombotic syndrome could occur.

Potential side effects of enoxaparin include fever, nausea, diarrhea, fluid retention, elevated LFTs, decreased platelets, decreased RBCs, local irritation, hematoma and redness.

A potential side effect of all direct oral anticoagulant treatment includes bleeding. Edoxaban also reported a rash, abnormal liver function tests, and anemia. Dabigatran is also associated with gastritis-like symptoms in 15% of patients.

**Rare:**

**Blood Sampling:** In rare circumstances venipuncture can cause blood clots, peripheral nerve injury or an arterial puncture.

**Anticoagulation:** The anticoagulation medication prescribed from the treating provider as planned treatment for catheter-related thrombosis can rarely cause bleeding requiring hospital admission, transfusion, or death.

**Breach of confidentiality:** personal health information will be collected and rarely a breach of confidentiality may lead to disclosure of that information.

In addition to the above possible risks, there is always the risk of developing previously unknown side effects.

## 10. Data

### 10.1 Data Management

The data gathered will be entered into REDCap data system with each ID having a unique identifier for each participant. REDCap is a secure, web-based application for building and managing online databases. All data will be de-identified and samples will only have a unique identifier that will link the unique identifier with the patient's name.

### 10.2 Data Collection

Research information, including consent forms and PTS assessments will be maintained secure as described in the Confidentiality section 8.3.

Each participant will be identified with a unique identifier number in REDCap. This unique identifier will be linked to the same unique identifier for a biological specimen sample stored in the [name] laboratory or the TRU to allow batched testing.

### 10.3 Data Monitoring

The PI or study staff will review all data collection forms on an ongoing basis for data completeness, accuracy, and protocol compliance. The data will be continuously monitored by the principal investigator of the study. The regulatory officer that is a part of the BCW Clinical Trials Office will assist with internal and external audits as appropriate. If protocol compliance or data accuracy comes into question study PI will request a study review.

Subject accrual, compliance with the protocol, status of enrolled subjects, adherence data regarding study visits, and adverse events will be summarized on a quarterly basis (or more frequently if needed) and reviewed by the PI. Serious adverse events will be reviewed at the time of the

occurrence by the PI and reported to the DSMC and IRB as per standard operating procedure.

A biannual safety and progress report will be submitted to the DSMC. The report will include the number of patients entered, number of patients treated, summary of all adverse events reported to date using standardized grading, a specific list of all serious adverse events [SAEs].

Data safety and monitoring activities for each study will continue until all patients have completed their treatment and the 6 months of follow-up. In the event that data and safety monitoring results in the suspension or termination of enrollment and/or treatment of patients, the principal investigator, the MCW CCC Director, the MCW Associate Director for Clinical Medical College of Wisconsin Cancer Center Research, the MCW IRB will be notified per MCW Office of Research Standard Operating Procedure.

The PI is responsible for the overall conduct of the project. Prior to start of the project at OSU, the PI will visit the site to ensure staff training, data management, and monitoring procedures are in place. Weekly or as needed teleconferences will be arranged between the study staff and investigators between OSU and WI to discuss enrollment, monitoring, concerns and trouble shoot any problems that arise. Audits of study procedures will be completed through WI institutional review boards and BCW clinical trials offices.

#### **10.4 Stopping Rules**

The DSMC can consider stopping the study prior to completion if:

1. The intervention is associated with adverse events that call into question the safety of the intervention
  - a. Interim analysis after 20 patients shows an incidence of thrombotic recurrence >40% (8/20 patients)
    - i. Rationale: A retrospective review of CRT in patients with hematologic malignancy at MCW found development of thrombosis other than CRT or extension of the catheter-related thrombosis in 20/141 (14%) of patients. Recurrent thrombosis has been reported in other studies in 20% of cancer patients. If after half of patients are recruited, the thrombotic incidence has doubled over the reported incidence in the literature, the study will be stopped. This level was chosen because it would be unlikely that if 8 events in the first 20 patients occur that no thrombotic events would occur in the next 20 patients to have an overall 20% (8/40) recurrent thrombosis incidence.

2. Difficulty in study recruitment or retention will significantly impact the ability to evaluate the study endpoints
3. New information becomes available that necessitates stopping the trial

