## **2. Study Objectives**

### **2.1 Feasibility Objectives:**

- 1) To determine the feasibility of a multicenter prospective cohort study of cancer patients with catheter-related thrombosis treated with 1 month of anticoagulation.
  - a. Feasibility will be defined as accrual of 56 patients in 1 year and 80% completion of PTS assessments
- 2) To determine the feasibility of obtaining plasma samples for biomarker analysis to predict recurrent venous thrombosis
  - a. Feasibility will be defined as obtaining 80% of plasma samples for biomarker analysis

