## **4.2 Selection of Subjects**

Subjects will be recruited at MCW and OSU through referral from their treating Hematologist or Oncologist. The patient's treating physician will give potential participants the informational flyer (Appendix A) or use the flyer to verbally describe the study and receive permission for the patient to be screened for eligibility and contacted by the research coordinator. Additionally at Milwaukee and Columbus, an electronic alert will be created that identifies a person with catheter-related thrombosis through the results of their radiology report. The research coordinator will review the report and then contact the treating physician to inform them of the study and receive permission to contact the subject. In 2012, 2350 new patients were seen in the Heme/Onc and BMT clinics at Froedtert Hospital and 1003 had a Port-A-Cath placed. Estimating a catheter-associated thrombotic rate of 15%, this predicts approximately 150 patients annually with CRT due to a Port-A-Cath. Additional patients are anticipated due to CRT from peripherally inserted central catheters (PICC). A survey was conducted among the Heme/Onc and BMT physicians at MCW with a 60% response rate (21/35). The physicians estimated that 63 patients had been seen with CRT in the last 3 months (252 annual). 86% of physicians reported that they would refer patients to a study of CRT treated with 4 weeks of anticoagulation; 14% were uncertain. MCW physicians also noted a variety of treatment practice from 4 weeks to 3 months of anticoagulation after catheter removal. We estimate a 10% drop out rate due to reinsertion of a catheter or inability to remove a catheter. We also estimate that we will need to screen and approach 3 patients for every participant. Therefore, we will plan to screen and approach 250 patients to enroll 56 patients (36 BCW and, OSU 20,) and have 50 complete the study as the overall target.

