## **4.3 Sample Size Estimates**

Sample size estimates were based on the confidence interval method and were based upon the feasibility endpoints. With 50 patients completing the study, we would have 95% confidence that completion of 80% of PTS assessments in the pilot study would correspond to 66-90% completion in another study. Completion of 90% of assessments

would correspond to between 78-96% of assessments. We estimate a 10% drop-out rate so will plan to enroll 56 patients over 1 year.

Evaluation of 50 patients would provide 95% confidence that if the feasibility study found a PTS incidence of 10% that the true proportion in a larger study would not be greater than 20%.

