### **11.2 Statistical Analysis**

The incidence of PTS, thrombotic recurrence, major bleeding and clinically relevant non-major bleeding will be reported as proportions. These outcomes will be compared at 3 and 6 months using Chi-square or Fisher's exact tests. A Cox-proportional hazards model will be utilized to calculate the risk of PTS and thrombosis recurrence. Chi-square or Fisher's exact tests will be used to determine if clot presentation or location predicts PTS or thrombotic recurrence. Agreement between the DASH and QuickDASH scales will be assessed using the intraclass correlation coefficient. To compare the discriminating ability of the DASH and QuickDASH on the level of PTS, receiver operating curves will be developed using the scale scores at 6 months as the test variable and dichotomized PTS assessment as the classifying variable. Levels of D-dimer, thrombin generation, and TFPI will be reported as means. Logistic regression will evaluate if D-dimer, thrombin generation or TFPI levels at 1 month or % change from baseline predict thrombotic recurrence. Where necessary, for parametric assumption, we will employ appropriate transformations with justifications. For example, the log of some of the biomarkers data may be used if the data range is >1000. Statistical

significance will be determined with  $p < 0.05$ . SAS version 9.13 and JMP 10 Statistical software will be employed for data analysis.

An interim analysis will be completed after 20 patients complete 6 months of follow-up. The interim analysis will allow assessment of thrombotic recurrence by the DSMC.

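### The interim stopping rule for recurrent thrombosis contradicts itself on threshold, consequence and timing, and its rationale assumes 40 patients where 56 are planned

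*Combined protocol and SAP*

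**What the plan says.** Section 10.4 opens with "The DSMC can consider stopping the study prior to completion if" and lists, as its one numerical criterion, "Interim analysis after 20 patients shows an incidence of thrombotic recurrence >40% (8/20 patients". The rationale beneath it cites two reference rates for recurrence: 20/141 (14%) from a local retrospective review and 20% from other studies. It then says "If after half of patients are recruited, the thrombotic incidence has doubled over the reported incidence in the literature, the study will be stopped". It defends the level by arguing that, after 8 events in the first 20 patients, it is improbable that "no thrombotic events would occur in the next 20 patients to have an overall 20% (8/40) recurrent thrombosis incidence".

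Section 11.2 describes the same look differently: "An interim analysis will be completed after 20 patients complete 6 months of follow-up".

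The planned size appears elsewhere. Section 4.3 says "We estimate a 10% drop-out rate so will plan to enroll 56 patients over 1 year", section 4.2 aims to "have 50 complete the study as the overall target", and section 2.1 makes accrual of 56 in one year part of the feasibility definition.

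**The concern.** A stopping boundary is written in advance so that nobody has to argue about its meaning once the events are known. This one leaves four things to argue about.

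- **Threshold.** The percentage and the count beside it are different rules.
- **Consequence.** The opening sentence lets the data safety monitoring committee (DSMC) consider stopping. The rationale says the study stops.
- **Size.** The rationale treats 20 patients as half the study and projects to 40. The plan is 56 enrolled and 50 completing.
- **Timing and cohort.** Section 10.4 speaks of half of patients being recruited, section 11.2 of 20 patients with 6 months of follow-up. Neither says whose events are counted in the 20, or what happens to a recurrence in a patient who is later removed (for example under section 5.4, for a new catheter) or who dies.

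The boundary guards against excess recurrence on a one-month course. Section 9.7 itself says that a shortened course could increase the risk of thrombosis. The bleeding and post-thrombotic outcomes have no numerical stopping threshold in the text available for review.

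**Working it through.** **Inputs.** Boundary above 40%, printed with 8/20 (10.4). Reference rates 20% and 20/141 = 14.2% (10.4). Plan: 56 enrolled in 12 months, 50 completing, 10% drop-out (4.2, 4.3). Look after 20 patients with 6 months of follow-up (11.2). No error rate, power or boundary method is stated for this rule, so there is no formal design to reproduce.

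**1. The plan's own figures.** 8/20 = 40.0%, which is not above 40%. The smallest count that is above it is 9/20 = 45.0%. 8/40 = 20% is correct arithmetic, but only for 40 patients. 50/(1 − 0.10) = 55.6, rounded up to 56, so 56 and 50 agree with each other and 40 matches neither.

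**2. What the threshold conflict changes.** With X ~ Binomial(20, p):

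| True risk p | P(X ≥ 8) | P(X ≥ 9) | P(X = 8), the difference |
|---|---|---|---|
| 20/141 | 0.4% | 0.1% | 0.3% |
| 20% | 3.2% | 1.0% | 2.2% |
| 30% | 22.8% | 11.3% | 11.4% |
| 40% | 58.4% | 40.4% | 18.0% |

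The last column is computed directly, so it can differ from the rounded columns by 0.1.

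**3. The rationale at the planned size.** Twenty patients are 20/50 = 40% of completers or 20/56 = 36% of enrolment, not half. Eight events and none afterwards give 8/50 = 16.0% or 8/56 = 14.3%, not 20%. An overall rate of at most 20% leaves room for 2 more events in the remaining 30 (10/50 = 20%) or 3 more in the remaining 36 (11/56 = 19.6%). The probability of staying within that room after 8/20 is:

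| True risk | As stated, 0 of 20 | N = 50, at most 2 of 30 | N = 56, at most 3 of 36 |
|---|---|---|---|
| 20% | 0.8^20 = 1.2% | 4.4% | 5.2% |
| 20/141 | (121/141)^20 = 4.7% | 18% | 23% |

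The claim of improbability survives at 20%. At the protocol's own local rate it is much weaker.

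**4. The two timings.** Assume even accrual of 56 in 12 months, r = 56/12 = 4.67 a month, with catheter removal at enrolment.

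- Half of 56 is 28 patients, recruited at 28/4.67 = month 6.0.
- The look in 11.2 comes at 20/[(1 − d) × r] + 6. With drop-out d = 0 this is 4.3 + 6 = month 10.3. With d = 10% it is 4.8 + 6 = month 10.8.
- Enrolled by then: 4.67 × 10.29 = 48, or 4.67 × 10.76 = 50, of 56.

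So the two descriptions place the same look more than 4 months apart under planned accrual.

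**The case against.** The strongest reply is that the meaning is recoverable and little depends on it. The printed count, the 8 in the rationale and the doubling of 20% all point to 8/20, so the strict inequality may be a slip. The opening sentence is permissive, and section 9.6 lets the DSMC terminate the study if it is unsafe, so 7, 8 or 9 events could all be acted on. Other oversight continues: monthly review of adverse events by the principal investigator (9.3), reporting of serious and unexpected events to the DSMC (9.4), and twice-yearly DSMC reports (9.6, 10.3). The gap between 58% and 40% needs a true risk twice the literature rate.

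Most of this stands, and it limits the size of the point. It does not remove it. A probable slip in a decision rule still needs correcting, and the automatic wording of the rationale denies the very discretion that the reply relies on.

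Three stronger readings are tempting, and the documents support none of them.

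- A reader might infer that section 11.2 makes completers the denominator, so that a fatal recurrence drops out of the count. That sentence fixes when the look takes place, not whose events count. A fatal recurrence would in any case be a serious adverse event (9.1) reported to the DSMC.
- A reader might infer that the look is wrong because it falls late in accrual. That is largely a design preference, and the dates in step 4 depend on even accrual. The inconsistency is only that 10.4 and 11.2 describe different moments.
- A reader might infer that recurrence goes unmonitored if the boundary is unclear. The routes listed above show otherwise.

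**Conclusion.** The rule is wrong as written and should be fixed. Section 10.4 gives opposite answers at 8 events, states two consequences, and argues from a study of 40 that is not the one planned. It also disagrees with section 11.2 on when the look occurs, and the cohort behind the 20 is left unstated.

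The arithmetic in steps 1 and 3 on the printed fractions needs no assumption. The trigger probabilities assume independent patients with a common risk and exactly 20 in the denominator. The timing figures assume even 12-month accrual and removal at enrolment.

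The effect is modest. The threshold conflict bites only at exactly 8 events, with probability 2.2% or 0.3% at the two cited rates and 18% if the true risk is 40%. DSMC discretion and routine safety reporting soften it further.

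**What to change.** Reconcile sections 10.4 and 11.2 so that they state one rule:

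- one boundary, with the percentage and the event count in agreement;
- one consequence, either DSMC consideration or an automatic stop;
- one cohort and denominator, including how a recurrence is handled in a patient later removed or deceased;
- one time for the look.

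Then restate the rationale for 50 to 56 patients, showing the result at both cited rates, 20% and 20/141. The sponsor and the DSMC should choose the boundary and its consequence; this point does not favour either reading.

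The cost is protocol wording and the amendment that carries it. No change in sample size, visits or data collection is needed.

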## **11. Statistical Considerations**

### **11.1 Description of Endpoints:**

#### **1. 11.1.1 Feasibility Endpoints:**

- a. Recruitment of 56 patients in 1 year and 80% completion of PTS assessments by enrolled patients.
- b. Feasibility of obtaining plasma samples for biomarker analysis as determined by obtaining 80% of samples from enrolled patients.

#### **11.1.2 : Clinical Endpoint**

2. Incidence of post-thrombotic syndrome <20% at 6 months.

#### **11.1.3: Secondary Endpoints**

1. Recurrent thrombosis
2. Incidence of major and clinically relevant non-major bleeding
3. Reliability of QuickDASH questionnaire in patients with catheter-related thrombosis

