syndrome using the modified Villalta scale (Appendix I) and functional limitation using the DASH questionnaire (Appendix J). At MCW, surveys will be administered by the TRU staff and physical examination will be completed by BCW nurse coordinator, [name]. At OSU, surveys will be administered by research coordinators trained to complete the assessment. Laboratory samples will be obtained for MCW participants only and processed as noted in section 5.6 and section 6.

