### 5.5 Post-thrombotic syndrome assessments

Visit 2 will occur within 2 weeks of discontinuation of anticoagulation. Visit 3 will be at 3 months after catheter removal plus or minus 2 weeks and Visit 4 within 6 months plus or minus 2 weeks after catheter removal. At each visit, medical history and medication will be reviewed (Appendices E-G). The subjective assessment of the modified Villalta (page 1 and 2 of Appendix I) and the DASH questionnaire (Appendix J) will be administered by the Translational Research Unit (TRU) staff or the clinical nurse coordinator after completing the objective assessment. The objective assessment of the modified Villalta score will be completed by trained clinical nurse coordinators blinded to the subjective assessment (page 3 and 4 of Appendix I). The subjective assessment of the modified Villalta (page 1 and 2 of Appendix I) and the DASH questionnaire (Appendix J), will be administered by the research coordinator at OSU.

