**Table 2. Study Schedule of Procedures**

Procedure	Screening	Visit 1 (Consent)	Visit 2	Visit 3	Visit 4
Review Eligibility criteria	X	X			
Consent for research participation		X			
Documentation-medical history, medications, &		X	X	X	X

clinical data					
Physical Examination			X	X	X
PTS Assessment: modified Villalta, DASH			X	X	X
Blood draw- D-dimer, thrombin generation, TFPI, plasma free DNA (MCW Only)			X	X	X

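### The QuickDASH reliability endpoint has no analysis that estimates reliability: section 11.2 plans only agreement with the DASH and discrimination of PTS

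*Combined protocol and SAP*

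**What the plan says.** Section 11.1.3 names three secondary endpoints. The third is "Reliability of QuickDASH questionnaire in patients with catheter-related thrombosis".

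Section 11.2 gives the QuickDASH two analyses:

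- "Agreement between the DASH and QuickDASH scales will be assessed using the intraclass correlation coefficient". The visit, the form of the ICC and an acceptable value are not stated.
- "To compare the discriminating ability of the DASH and QuickDASH on the level of PTS, receiver operating curves will be developed", with the 6-month scale scores as test variable and dichotomized PTS as classifier.

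No internal-consistency, test-retest or inter-rater analysis of the QuickDASH is planned.

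The QuickDASH is named only in sections 11.1.3 and 11.2. Where data collection is described, the instrument is the DASH. Section 4.1 names the DASH for functional limitation at each visit. Section 5.5 names it for both sites, for example "the DASH questionnaire (Appendix J), will be administered by the research coordinator at OSU". The row in Table 2, marked for Visits 2, 3 and 4, reads "PTS Assessment: modified Villalta, DASH".

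**The concern.** Reliability of a questionnaire is its consistency with itself, either across its items at one time or on repetition in people who have not changed. Agreement between a short form and a longer parent scale is a different property. A short form can track its parent closely and still be a noisy measure, particularly if both scores come from the same answers.

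As written, a named endpoint has no analysis that estimates it. The risk is one of interpretation: a DASH-QuickDASH ICC could be reported under the reliability endpoint and read as evidence that the short form is reliable in this population.

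**Working it through.** **Plan's own figure.** There is none to reproduce. The documents give no target ICC, precision or sample size for this endpoint, and the sample size in section 4.3 rests on the feasibility endpoints.

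**Endpoint against analyses.**

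| Planned analysis (11.2) | What it estimates | Reliability? |
|---|---|---|
| ICC, DASH with QuickDASH | Agreement between two scales | No |
| ROC curves against PTS at 6 months | Discrimination | No |

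**Where a QuickDASH score would come from.** Sections 4.1 and 5.5 and Table 2 schedule only the DASH. The simplest reading is that a subset of DASH items is rescored as the QuickDASH. That is an inference. Appendix J is not in the text available, so its contents cannot be checked.

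**What follows if it is rescored.** Assumptions, none of them from the documents: a full scale of n = 30 items, a short form of k items contained in it, equal item means and variances, and a common inter-item correlation r. For scores that are item means:

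- Short-form variance: vS = r + (1 − r)/k
- Full-scale variance: vF = r + (1 − r)/n
- Covariance, because the k items are part of the n: r + (1 − r)/n
- ICC = 2[r + (1 − r)/n] / (vS + vF)
- Cronbach's alpha of the short form = r/vS

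Worked case, k = 11 and r = 0.2:

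- vS = 0.2 + 0.8/11 = 0.2727
- vF = 0.2 + 0.8/30 = 0.2267
- ICC = 2 × 0.2267/(0.2727 + 0.2267) = 0.91
- alpha = 0.2/0.2727 = 0.73

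| r (k = 11) | alpha | ICC with DASH | Gap |
|---|---|---|---|
| 0 | 0 | 0.54 | 0.54 |
| 0.1 | 0.55 | 0.83 | 0.28 |
| 0.2 | 0.73 | 0.91 | 0.18 |
| 0.3 | 0.83 | 0.94 | 0.12 |
| 0.5 | 0.92 | 0.97 | 0.06 |

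Gaps are taken from unrounded values. Other short-form lengths at r = 0.2 give alpha 0.67 against ICC 0.86 (k = 8) and 0.79 against 0.94 (k = 15).

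**Contribution of shared answers.** If the QuickDASH were given separately, with independent item errors, the covariance would fall to r. For k = 11 and r = 0.2 the ICC would be 2 × 0.2/(0.2727 + 0.2267) = 0.80 rather than 0.91. It would still be an agreement coefficient.

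**Could the scheduled visits serve as a retest?** Section 5.5 says "Visit 3 will be at 3 months after catheter removal plus or minus 2 weeks", and Visit 4 falls at 6 months with the same tolerance, so the two are about three months apart. The patients are under active cancer treatment (section 3.2), so arm function may truly change. Limiting the analysis to patients with unchanged PTS category does not hold function constant. It may also restrict the range: at the 10% PTS incidence used for illustration in section 4.3, 45 of 50 completers would have no PTS. Both effects lower the coefficient. Precision would also be modest. With all 50 completers, a Fisher z interval (SE = 1/√48.5 = 0.144) around an ICC of 0.70 runs from 0.53 to 0.82.

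**The case against.** The strongest defence is that section 11.2 itself calls the analysis agreement, so a report that follows it would describe agreement and nobody need be misled. The ROC comparison is a further evaluation of the short form that does not depend on the ICC. This is also the third secondary endpoint of a pilot whose success criteria lie elsewhere. All of that is fair and limits the importance of the point. It does not supply an analysis for the endpoint as named.

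Three stronger readings are tempting, and the documents do not support them.

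- **That the ICC is bound to look too good.** This needs the QuickDASH to be scored from the same DASH answers at the same visit, and the plan states neither. Even under that reading, the size depends on item numbers and correlations that the documents do not give. At r = 0.5 the short form is itself reliable and the gap is small. At r = 0 the ICC is 0.54, which few would call high.
- **That the missing QuickDASH row makes the endpoint unobtainable.** If the score is derived from DASH items, no separate row is needed. What is missing is a sentence saying so.
- **That the later trial would adopt the QuickDASH on this result.** Section 1 says the pilot will inform sample size and the choice of anticoagulation durations to compare. It does not mention choosing a questionnaire.

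**Conclusion.** The mismatch is established from the text alone: the endpoint is reliability, and the planned analyses estimate agreement and discrimination. It holds however the QuickDASH is obtained.

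Inflation of the ICC above the short form's own reliability is conditional on shared answers. Under the equal-correlation illustration with 11 of 30 items, the gap is 0.18 at r = 0.2 and 0.06 at r = 0.5. These figures show direction only and do not predict this study's result.

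The point is worth correcting because correction is nearly free and changes what the endpoint can conclude. It has no bearing on accrual, completion of assessments, plasma sampling, PTS incidence or the number enrolled.

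**What to change.** In section 11.2:

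1. State that the QuickDASH is scored from the DASH items, listing the items and the rule for missing answers. If it is instead meant to be given separately, add it to section 5.5 and Table 2.
2. Assess the reliability endpoint with Cronbach's alpha of the QuickDASH items, with a 95% confidence interval, at each of Visits 2, 3 and 4. Say that this addresses internal consistency and not reproducibility.
3. Relabel the DASH-QuickDASH ICC as agreement of the short form with its parent scale. Give the visit and the ICC form, add the mean difference and limits of agreement, and do not report it as reliability.
4. Keep any ICC of the QuickDASH between Visits 3 and 4 as exploratory, noting that true change and restricted range would lower it.

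If alpha is not wanted, the minimum is to rename the endpoint in section 11.1.3 as agreement of the QuickDASH with the DASH.

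Cost: a few sentences and a few lines of code. If the QuickDASH is scored from the DASH, no new questionnaire or visit is needed. The downside is slightly more analysis and a reliability figure that may be less favourable than the ICC.
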